During the study, male subjects with female partners of childbearing potential should use condoms until 30 days after the last dose of LDV/SOF treatment when engaging in intercourse of reproductive potential. If their female partner is of childbearing potential (as defined above), their female partner must use 1 of the methods of birth control listed above from the date of Screening until 30 days after the last dose of LDV/SOF.

4) Unacceptable Birth Control Methods

Birth control methods that are unacceptable include periodic abstinence (e.g., calendar, ovulation, symptothermal, post-ovulation methods), withdrawal (coitus interruptus), spermicides only, and lactational amenorrhea method (LAM). Female condom and male condom should not be used together.

5) Procedures to be Followed in the Event of Pregnancy

Subjects will be instructed to notify the investigator if they become pregnant at any time during the study, or if they become pregnant within 30 days of last dose of LDV/SOF. Subjects who become pregnant or who suspect that they are pregnant during the study must report the information to the investigator and discontinue study drug immediately. Subjects whose partner has become pregnant or suspects she is pregnant during the study must report the information to the investigator. Instructions for reporting pregnancy, partner pregnancy, and pregnancy outcome are outlined in Section [7.5.2.1](#).

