4.1. Inclusion Criteria

Subjects must meet all of the following inclusion criteria to be eligible for participation in this study.

- 1) Willing and able to provide written informed consent
- 2) Male or female age \geq 18 years
- 3) Chronic HCV infection (\geq 6 months) as documented by prior medical history or liver biopsy
- 4) HCV RNA \geq LLOQ at screening
- 5) Genotype 1,4, 5, and 6 HCV as determined at Screening
- 6) End stage renal disease (ESRD) requiring peritoneal dialysis (PD) or hemodialysis (HD)
- 7) The most recent HCV treatment must have been completed at least 8 weeks prior to screening
- 8) Subjects must have a determination of treatment experience (treatment naïve vs. treatment experienced). Treatment naïve is defined as having never been exposed to an approved or experimental HCV-specific direct acting antiviral agents or prior treatment of HCV with interferon or ribavirin. All other subjects will be considered treatment experienced.
- 9) Subjects must have appropriate testing for determination of cirrhosis status.
 - a) Presence of cirrhosis is defined as any one of the following:
 - i) Fibroscan with a result of > 12.5 kPa
 - ii) Liver biopsy showing cirrhosis (e.g., Metavir score = 4 or Ishak score \geq 5)
 - iii) In the absence of liver biopsy or availability of Fibroscan, FibroTest[®] score ≥ 0.75 at screening
 - b) Absence of cirrhosis is defined as any one of the following:
 - i) Fibroscan with a result of ≤ 12.5 kPa within ≤ 6 months of Baseline/Day 1
 - ii) Liver biopsy performed within 2 years of Screening showing absence of cirrhosis
 - iii) In the absence of liver biopsy or availability of Fibroscan, FibroTest[®] score < 0.75 at screening

- 10) Liver imaging within 6 months of Baseline/Day 1 is required in cirrhotic subjects only, to exclude HCC
- 11) Subjects with HIV-1 coinfection may be eligible, provided they satisfy these additional inclusion criteria:
 - i) Completed at least 3 months of any prior HIV ARV therapy and maintained HIV RNA<50 copies/mL (or <LLOQ if the local laboratory assay's LLOQ is $50 \geq$ copies/mL) and CD4 T-cell count > 100 cells/mm³ prior to Screening. Subjects with an isolated or unconfirmed HIV RNA >50 copies/mL (or $>LLOQ$ if the local laboratory assay's LLOQ is $50 \geq$ copies/mL) are not excluded
 - ii) On a stable ARV regimen for ≥ 8 weeks prior to Screening and is expected to continue the current ARV regimen through the end of study (See exclusion criteria 16).

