6.3. Treatment Assessments

6.3.1. Week 2 (\pm 3 days): Group 1, 2, and 3

The following procedures/assessments are to be completed at the end of Week 2:

- Obtain vital signs
- Assessment of AEs and concomitant medications

- Obtain blood samples for:
 - Hematology
 - Chemistry
 - HCV RNA
 - Viral sequencing/phenotyping
 - Sparse PK sample
- Assess adherence with study drug dosing regimen including pill count

6.3.2. Week 4 (\pm 3 days): Group 1, 2, and 3

The following procedures/assessments are to be completed at the end of Week 4:

- Obtain vital signs
- Assessment of AEs and concomitant medications
- Conduct pregnancy prevention counselling
- Obtain blood samples for:
 - Hematology
 - Chemistry
 - HCV RNA
 - Viral sequencing/phenotyping
 - Sparse PK sample
 - Serum β -hCG pregnancy test for females of childbearing potential only
 - HIV-1 RNA and CD4 cell count will only be collected and analyzed for HIV co-infected subjects
 - HBV DNA (only in subjects who are HBcAb+ at Screening)
- Assess adherence with study drug dosing regimen including pill count
- Dispense study drug as directed by the IWRs

6.3.3. Week 6 (\pm 3 days): Group 1, 2, and 3

The following procedures/assessments are to be completed at the end of Week 6:

- Obtain vital signs
- Assessment of AEs and concomitant medications
- Obtain blood samples for:
 - Hematology
 - Chemistry
 - HCV RNA
 - Viral sequencing/phenotyping
 - Sparse PK sample
 - Intensive PK (for subjects who have consented)
 - Hemodialysis PK (for subjects who have consented)
- Assess adherence with study drug dosing regimen including pill count

6.3.4. Week 8 (\pm 3 days): Group 2 and 3 (For Group 1 Week 8, see End of Treatment Visit)

The following procedures/assessments are to be completed at the end of Week 8 for Groups 2 and 3 only:

- Obtain vital signs
- Assessment of AEs and concomitant medications
- Conduct pregnancy prevention counselling
- Obtain blood samples for:
 - Hematology
 - Chemistry
 - HCV RNA
 - Viral sequencing/phenotyping

- Sparse PK sample
- Serum β-hCG pregnancy test for females of childbearing potential only
- HIV-1 RNA and CD4 cell count will only be collected and analyzed for HIV co-infected subjects
- HBV DNA (only in subjects who are HBcAb+ at Screening)
- Intensive PK (for subjects who have consented)
- Hemodialysis PK (for subjects who have consented)
- Assess adherence with study drug dosing regimen including pill count
- Dispense study drug as directed by the IWRs

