6.9. Procedures and Specifications

6.9.1. Clinical Laboratory Analytes

Hematology: Hematocrit, hemoglobin (Hb), platelet count, red blood cell count (RBC), white blood cell count (WBC) with differential (absolute and percentage) including lymphocytes, monocytes, neutrophils, eosinophils, basophils, reticulocyte count and mean corpuscular volume (MCV).

Coagulation: INR, Prothrombin time (PT), Activated partial thromboplastin time (APTT)

Chemistry: Alanine aminotransferase (ALT/SGPT), aspartate aminotransferase (AST/SGOT), albumin, alkaline phosphatase, creatinine, total bilirubin, direct bilirubin; glucose, potassium, and sodium. Fibrotest® will be done at screening only.

Virological Tests: Serologies for HCV and HBV (HBsAg, HBsAb, and HBcAb). HBV DNA (only in subjects who are HBcAb+ at Screening). Serology testing for HIV (including reflex testing as necessary), HCV RNA will be measured using the COBAS® AmpliPrep/COBAS® TaqMan® HCV Test, v2.0 for Use with the High Pure System, HCV genotype and subtype will be determined using the Siemens VERSANT® HCV Genotype, INNO-LiPA 2.0 Assay. HIV-1 RNA will be measured using the AmpliPrep/COBAS® TaqMan® HIV-1 Test, v2.0. If HIV-1 virologic rebound is confirmed, HIV-1 genotype/phenotype will be determined using the PhenoSense™ Integrase HIV, GeneSeq™ Integrase HIV, PhenoSense™ HIV, GenoSure MG, GeneSeq™ HIV, and PhenoSense GT™.

Gilead reserves the right to use alternate assays for HCV RNA, HIV RNA, HCV genotype, and HIV-1 genotype/phenotype should the above assays become unavailable or the results are not definitive.

IL28B genotype will be determined by polymerase chain reaction (PCR) amplification of the SNP, rs12979860, with sequence specific forward and reverse primers and allele specific fluorescently labeled TaqMan® MGB probes. Gilead reserves the rights to use alternate assays for IL28B determination should the above assay become unavailable.

Pregnancy Tests: Serum β-hCG

Additional Tests: Serum drug screen (for amphetamines, cocaine, methadone, opiates), HbA1c, CD4 T-lymphocyte (absolute count and %)

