Serum Drug Screen	X												
HCV & IL28B Genotyping	X												
HCV, HIV, HBV Serology	X												
HBV DNA ^k		X		X		X	X	X	X	X	X	X	X
HbA1c	X												
Fibrotest [®]	X												
Archive Sample ^f		X								X			
Pharmacogenomic Sample ^f		X											
CD4 Cell Count ^l	X	X		X		X	X	X	X	X	X		
HIV-1 RNA ^l	X	X		X		X	X	X	X	X	X		

a Baseline/Day 1 assessments must be performed prior to dosing

b Only SAEs will be collected at post-treatment Weeks 12 and 24.

c Health Related Quality of Life (HRQoL) Surveys (e.g., SF-36, CLDQ-HCV, FACIT-F and WPAI) will be conducted for all subjects where the surveys are available at Day 1, Week 24, ET (if applicable), and posttreatment Week 12.

d The IWRS will provide direction on the specifics of each subject's study drug dispensing

e Plasma samples will be collected for possible viral resistance testing and other virology studies

f Subjects may opt out of archive/pharmacogenomics sample collection.

g Only for subjects who have provided consent for this sample and testing.

h Intensive PK evaluations will be assessed at the following timepoints: 0 (pre-dose -5 minutes), 0.25, 0.5, 1, 2, 4, 6, 8, 10, and 12 hours post dose once either on Week 6-8, or 12 per investigator discretion.

i Hemodialysis PK blood samples will be collected at one hemodialysis session between Week 6 and Week 12, inclusive (as appropriate based on treatment regimen), evaluations will include: 1. A single blood sample will be collected within 10 minutes before hemodialysis initiates. 2. During hemodialysis, a single sample will be collected from both the arterial and venous sides of the dialyzer within 1 hour of hemodialysis concluding. 3. Finally a single blood sample will be collected within 10 minutes after hemodialysis concludes.

j For females of child bearing potential

k Only for subjects who are HBcAb+ at Screening

l For HIV/HCV co-infected subjects only.

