Appendix 3. GSI Grading Scale for Severity of Adverse Events and Laboratory Abnormalities

Antiviral Toxicity Grading Scale Version: 01 April 2015

HEMATOLOGY				
	Grade 1	Grade 2	Grade 3	Grade 4
Hemoglobin				
HIV POSITIVE	8.5 to 10.0 g/dL	7.5 to < 8.5 g/dL	6.5 to < 7.5 g/dL	< 6.5 g/dL
Adult and Pediatric \geq 57 Days	85 to 100 g/L	75 to < 85 g/L	65 to < 75 g/L	< 65 g/L
HIV NEGATIVE	10.0 to 10.9 g/dL	9.0 to < 10.0 g/dL	7.0 to < 9.0 g/dL	< 7.0 g/dL
Adult and Pediatric \geq 57 Days	100 to 109 g/L OR Any decrease from Baseline	90 to < 100 g/L OR Any decrease from Baseline	70 to < 90 g/L OR Any decrease from Baseline	< 70 g/L
	2.5 to < 3.5 g/dL 25 to < 35 g/L	3.5 to < 4.5 g/dL 35 to < 45 g/L	\geq 4.5 g/dL \geq 45 g/L	
Infant, 36–56 Days (HIV POSITIVE OR NEGATIVE)	8.5 to 9.4 g/dL 85 to 94 g/L	7.0 to < 8.5 g/dL 70 to < 85 g/L	6.0 to < 7.0 g/dL 60 to < 70 g/L	< 6.0 g/dL < 60 g/L
Infant, 22–35 Days (HIV POSITIVE OR NEGATIVE)	9.5 to 10.5 g/dL 95 to 105 g/L	8.0 to < 9.5 g/dL 80 to < 95 g/L	7.0 to < 8.0 g/dL 70 to < 80 g/L	< 7.0 g/dL < 70 g/L
Infant, 1–21 Days (HIV POSITIVE OR NEGATIVE)	12.0 to 13.0 g/dL 120 to 130 g/L	10.0 to < 12.0 g/dL 100 to < 120 g/L	9.0 to < 10.0 g/dL 90 to < 100 g/L	< 9.0 g/dL < 90 g/L
Absolute Neutrophil Count (ANC)	1000 to 1300/mm ³	750 to < 1000/mm ³	500 to < 750/mm ³	< 500/mm ³
Adult and Pediatric, \geq 7 Months[#]	1.00 to 1.30 GI/L	0.75 to < 1.00 GI/L	0.50 to < 0.75 GI/L	< 0.50 GI/L
Absolute CD4+ Count				
HIV NEGATIVE ONLY				
Adult and Pediatric $>$ 13 Years	300 to 400/mm ³ 300 to 400/ μ L	200 to < 300/mm ³ 200 to < 300/ μ L	100 to < 200/mm ³ 100 to < 200/ μ L	< 100/mm ³ < 100/ μ L

HEMATOLOGY				
	Grade 1	Grade 2	Grade 3	Grade 4
Absolute Lymphocyte Count HIV NEGATIVE ONLY Adult and Pediatric > 13 Years	600 to 650/mm ³ 0.60 to 0.65 GI/L	500 to < 600/mm ³ 0.50 to < 0.60 GI/L	350 to < 500/mm ³ 0.35 to < 0.50 GI/L	< 350/mm ³ < 0.35 GI/L
Platelets	100,000 to < 125,000/mm ³ 100 to < 125 GI/L	50,000 to < 100,000/mm ³ 50 to < 100 GI/L	25,000 to < 50,000/mm ³ 25 to < 50 GI/L	< 25,000/mm ³ < 25 GI/L
WBCs	2000/mm ³ to 2500/mm ³ 2.00 GI/L to 2.50 GI/L	1,500 to < 2,000/mm ³ 1.50 to < 2.00 GI/L	1000 to < 1,500/mm ³ 1.00 to < 1.50 GI/L	< 1000/mm ³ < 1.00 GI/L
Hypofibrinogenemia	100 to 200 mg/dL 1.00 to 2.00 g/L	75 to < 100 mg/dL 0.75 to < 1.00 g/L	50 to < 75 mg/dL 0.50 to < 0.75 g/L	< 50 mg/dL < 0.50 g/L
Hyperfibrinogenemia	> ULN to 600 mg/dL > ULN to 6.0 g/L	> 600 mg/dL > 6.0 g/L	— —	— —

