### **7.2.2. Graded Laboratory Values**

The Gilead Grading Scale for Severity of Adverse Events and Laboratory Abnormalities will be used for assigning toxicity grades to laboratory results for analysis as Grade 0, Grade 1 (mild), Grade 2 (moderate), Grade 3 (severe), or Grade 4 (potentially life threatening). Grade 0 includes all values that do not meet criteria for an abnormality of at least Grade 1. Some laboratory tests

have laboratory toxicity criteria for both increased and decreased levels; analyses for each direction (ie, increased, decreased) will be presented separately.

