#### 7.2.2.2. Summaries of Laboratory Abnormalities

Laboratory data that are categorical will be summarized using the number and percentage of subjects in the study with the given response at baseline and each scheduled postbaseline visit.

The following summaries (number and percentage of subjects) for treatment-emergent laboratory abnormalities will be provided by analyte; subjects will be categorized according to the most severe postbaseline abnormality grade for a given analyte:

- Graded laboratory abnormalities
- Grade 3 or above laboratory abnormalities

For all summaries of laboratory abnormalities, the denominator is the number of subjects with nonmissing postbaseline values up to 30 days after last dose of study drug for the laboratory parameter of interest.

A by-subject listing of treatment-emergent Grade 3 or above laboratory abnormalities will be provided by subject ID number and visit in chronological order. This listing will include all test results that were collected throughout the study for the analyte of interest, with all applicable severity grades or abnormal flags displayed.

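### Lymphocytes are graded in HIV-negative subjects only, but the SAP denominator counts everyone with a value, so any co-infected subjects dilute the graded lymphocyte rate

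*Protocol*

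**What the plan says.** **Grading scale.** The hematology part of Protocol Appendix 3 has a row headed "Absolute Lymphocyte Count HIV NEGATIVE ONLY Adult and Pediatric > 13 Years", with no counterpart for HIV-positive subjects. The absolute CD4+ count row carries the same restriction, "HIV NEGATIVE ONLY". Hemoglobin, in the same table, has separate HIV-positive and HIV-negative rows.

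**Who is measured.** Protocol 4.1 admits co-infected subjects: "Subjects with HIV-1 coinfection may be eligible, provided they satisfy these additional inclusion criteria". Protocol 6.9.1 includes in hematology, for every subject, a "white blood cell count (WBC) with differential (absolute and percentage) including lymphocytes". CD4 is different. Protocol 6.3 states that "HIV-1 RNA and CD4 cell count will only be collected and analyzed for HIV co-infected subjects", and the schedule footnotes in Appendix 2 agree: "For HIV/HCV co-infected subjects only".

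**How grades are summarised.** SAP 7.2.2 says that "Grade 0 includes all values that do not meet criteria for an abnormality of at least Grade 1". SAP 7.2.2.1 counts an abnormality as treatment-emergent when it rises at least one grade from baseline. SAP 7.2.2.2 then says, for all laboratory abnormality summaries, that "the denominator is the number of subjects with nonmissing postbaseline values up to 30 days after last dose of study drug" for the parameter in question. SAP 7.2 bases these summaries on the Safety Analysis Set, without a split by HIV status.

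**The concern.** The numerator and the denominator describe different populations. Only HIV-negative subjects can have a graded lymphocyte abnormality, while the denominator includes everyone with a lymphocyte value. A co-infected subject whose count fell below 350/mm³, which is Grade 4 for an HIV-negative subject, would be counted as a subject without an abnormality. That subject would also not trigger the SAP 7.2.2.2 listing of treatment-emergent Grade 3 or above abnormalities on the lymphocyte result.

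At stake is the reported percentage with treatment-emergent lymphocyte abnormalities, which can only move downward. Lymphocytes are among the analytes that SAP 7.2.1 summarises and plots. A reader of the tables could not easily undo the dilution, because HIV status is not among the baseline characteristics in SAP 5.2 or the subgroups in SAP 3.3.

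**Working it through.** The documents state no lymphocyte abnormality rate and no expected number of co-infected subjects, so there is no plan figure to reproduce.

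**Inputs**
- N, subjects with a postbaseline lymphocyte value: taken as 100, the approximate planned enrolment (Protocol 4).
- h, co-infected subjects among them: not in the documents; assumed 0, 2, 5, 10 or 20.
- k, HIV-negative subjects with a treatment-emergent graded lymphocyte abnormality: not in the documents; assumed 5, 10 or 15.

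**Step 1: can a co-infected subject enter the numerator?** A rise of at least one grade is needed. No lymphocyte criterion applies to these subjects, so under SAP 7.2.2 each of their values is Grade 0 and no rise can occur. The missing-baseline rule in SAP 7.2.2.1 does not change this, because it still needs a postbaseline value of at least Grade 1.

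**Step 2: do they leave the denominator?** No. SAP 7.2.2.2 asks only for a nonmissing postbaseline value, and hematology is scheduled at every visit.

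**Step 3: formula.**
- Reported rate = k/N.
- HIV-negative rate = k/(N - h).
- Hence reported rate = (1 - h/N) × HIV-negative rate, and the relative understatement is h/N.

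**Step 4: numbers.** Each cell gives k/(100 - h), with its difference from k/100 in percentage points.

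| h | k = 5 (reported 5.0%) | k = 10 (reported 10.0%) | k = 15 (reported 15.0%) |
|---|---|---|---|
| 0 | 5/100 = 5.0% (0) | 10/100 = 10.0% (0) | 15/100 = 15.0% (0) |
| 2 | 5/98 = 5.1% (0.1) | 10/98 = 10.2% (0.2) | 15/98 = 15.3% (0.3) |
| 5 | 5/95 = 5.3% (0.3) | 10/95 = 10.5% (0.5) | 15/95 = 15.8% (0.8) |
| 10 | 5/90 = 5.6% (0.6) | 10/90 = 11.1% (1.1) | 15/90 = 16.7% (1.7) |
| 20 | 5/80 = 6.3% (1.3) | 10/80 = 12.5% (2.5) | 15/80 = 18.8% (3.8) |

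Within a treatment group the same factor applies with that group's own h and N, so the shift would be larger in a group where co-infected subjects happened to cluster.

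**The case against.** The strongest reply is that the effect is small and conditional. It vanishes if no co-infected subject enrols. With few enrolled it is well inside the sampling error: the exact 95% interval for 15/100 runs from 8.6% to 23.5%, against a shift of 1.7 points at h = 10. The tables are descriptive, SAP 7.2 rules out inferential statistics, and counts appear beside percentages. All of this stands and limits the weight of the point.

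Low counts in co-infected subjects also stay visible elsewhere. SAP 7.2 flags listed values outside the reference range whether or not they are graded, and SAP 7.2.1 summarises and plots lymphocytes by visit for all subjects. This stands too, but those displays give no abnormality rate and do not correct the one reported.

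It can be said that SAP 7.2.2 never addresses values outside the scale's stated population, and that a programmer might leave them ungraded. That is possible. However, the Grade 0 rule covers all values meeting no criterion, and leaving a value ungraded would still not remove the subject from the stated denominator.

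The rate with denominator N - h is the HIV-negative rate. It is not a corrected overall rate, because lymphopenia in co-infected subjects is not graded at all. That is right, and it is why the restricted summary needs a label.

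A reader might go further and infer that the plan will report a graded CD4 row that is 0% whatever happens, falsely reassuring about the only subjects in whom CD4 is measured. The documents do not support this. Protocol 8.6 does name CD4 as a safety laboratory test. But Protocol 6.9.1 places it under additional tests rather than hematology, SAP 7.2.1 does not list it, and no section specifically plans a graded CD4 row. Such a table is hypothetical.

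**Conclusion.** The point holds for lymphocytes, as a minor inconsistency between the grading scale and the SAP's Grade 0 and denominator rules. Read as written, the SAP reports (1 - h/N) times the HIV-negative rate. For N = 100 and 5 to 15 events, the understatement is about 0.1 to 0.3 points at h = 2, about 0.6 to 1.7 points at h = 10, and zero at h = 0. Both h and the event count are assumptions. A flat statement that the rate is biased downward would go too far, because the dilution depends on co-infected subjects being enrolled. SVR12, the primary safety endpoint and the sample-size statement are untouched. For CD4 the documents support only a clarification that no graded row is to be produced.

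**What to change.** Add to SAP 7.2.2.2: *For analytes that Protocol Appendix 3 grades in HIV-negative subjects only, the numerator and denominator of the graded summary are restricted to HIV-negative subjects, and the summary is labelled accordingly. Values of these analytes in HIV co-infected subjects are treated as not graded, rather than Grade 0. Consequently no graded CD4 summary is produced.*

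This applies the scale's own restriction to both parts of the fraction and introduces no new threshold. The cost is a short SAP addition, a table label and a programming condition on HIV status. If co-infected subjects enrol and any graded abnormality occurs, the reported lymphocyte percentages will be slightly higher.

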Appendix 5. Opportunistic Infections

Non-inclusive list of opportunistic infections base on AIDS-Indicator Conditions from CDC Classification System for HIV Infection Clinical Category C:

- Bacterial pneumonia, recurrent (two or more episodes in 12 months)
- Candidiasis of the bronchi, trachea, or lungs
- Candidiasis, esophageal
- Cervical carcinoma, invasive, confirmed by biopsy
- Coccidioidomycosis, disseminated or extrapulmonary
- Cryptococcosis, extrapulmonary
- Cryptosporidiosis, chronic intestinal (>1 month in duration)
- Cytomegalovirus disease (other than liver, spleen, or nodes)
- Encephalopathy, HIV-related
- Herpes simplex: chronic ulcers (>1 month in duration), or bronchitis, pneumonitis, or esophagitis
- Histoplasmosis, disseminated or extrapulmonary
- Isosporiasis, chronic intestinal (>1-month in duration)
- Kaposi sarcoma
- Lymphoma, Burkitt, immunoblastic, or primary central nervous system
- *Mycobacterium avium* complex (MAC) or *Mycobacterium kansasii*, disseminated or extrapulmonary
- *Mycobacterium tuberculosis*, pulmonary or extrapulmonary
- *Mycobacterium*, other species or unidentified species, disseminated or extrapulmonary
- *Pneumocystis jiroveci* (formerly *carinii*) pneumonia (PCP)
- Progressive multifocal leukoencephalopathy (PML)
- *Salmonella* septicemia, recurrent (nontyphoid)
- Toxoplasmosis of brain
- Wasting syndrome caused by HIV (involuntary weight loss >10% of baseline body weight) associated with either chronic diarrhea (two or more loose stools per day for ≥ 1 month) or chronic weakness and documented fever for ≥ 1 month
